Music listening is one such intervention that holds promise for non-pharmacological management of delirium commonly experienced by mechanically ventilated patients. Music has been shown to break the harmful cycle of over-sedation in critically ill and can reduce anxiety and stress, factors that could predispose to ICU delirium. These findings are not surprising given that music results in a reduction in inflammatory cytokines, decreases cortisol production, and dampens central nervous system arousal through diminished norepinephrine release; pathways similar to those implicated in delirium. In a randomized clinical trial conducted by [name] (MPI), a music intervention consisting of patient-directed, slow-tempo, relaxing music delivered during the latter portion of mechanical ventilator support was superior to usual ICU care in reducing anxiety and sedative exposure in critically ill patients. Even with such positive findings both at mechanistic and patient-outcome levels, music listening interventions are notably absent in routine ICU care. Further, there is a paucity of rigorous investigation of music's impact on ICU delirium, a significant knowledge gap.

We now propose an adequately powered randomized clinical trial to test the efficacy of a seven-day music intervention in reducing delirium and improving brain health among critically ill, mechanically ventilated older adults through the following specific aims:

2. RATIONALE and SPECIFIC AIMS:

Critically ill patients on mechanical ventilation are at high risk to develop delirium and need innovative, safe and scalable interventions to ameliorate it. The scientific premise of our proposal is that early slow-tempo music listening in the ICU setting will reduce delirium among older adults, which will lead to downstream beneficial effects on long-term cognition. Music has been shown to be beneficial in managing pain and anxiety symptoms through anti-inflammatory and cortisol mediated pathways, similar pathways that are disrupted and implicated in delirium development. Additionally, slow-tempo music could also reduce exposure to opioids and sedative medications ubiquitous in the ICU setting and associated with delirium. Hence it stands to reason that a music intervention will be efficacious in reducing ICU delirium. Even with the clinical rationale and aforementioned data, a rigorous trial testing the efficacy of music intervention on ICU delirium is notably lacking.

Primary Specific Aim: Test the efficacy of music intervention in *improving delirium/coma free days* among mechanically ventilated patients as compared to attention control. Hypothesis: Patients in the music intervention group will have higher number of delirium/coma free days as measured by the Confusion Assessment Method for the ICU (CAM-ICU) at seven days post randomization.

Secondary Specific Aim 1: Test the efficacy of music intervention in *improving delirium severity, pain and anxiety* among mechanically ventilated patients as compared to attention control. Hypotheses: Patients in the music intervention group will have lower delirium severity, pain and anxiety scores as measured by the CAM- ICU-7, Critical Care Pain Observation Tool (CPOT) and Visual Analogue Scale-Anxiety (VAS-A) respectively at seven days post-randomization.

Secondary Specific Aim 2: Test the efficacy of music intervention in *improving the long-term neuro-psychological outcomes* as compared to attention control. Hypotheses: Patients in the music intervention group will have higher cognitive scores as assessed by the Indiana University Telephone Based Assessment of Neuropsychological Status (IU-TBANS), and lower depression and anxiety scores on the Patient Health Questionnaire (PHQ-9) and Generalized Anxiety Disorder (GAD-7) scales at 3 months post hospital discharge.

3. STUDY DESIGN

Two-arm, randomized parallel-group, clinical trial with concealment of outcomes assessment to evaluate the efficacy of music intervention compared to a silence-track attention control in improving delirium/coma free days in mechanically-ventilated critically ill older adults. The total duration of the intervention will be 7 days from randomization unless a patient has died, discharged, or transferred out of the ICU.

4. INCLUSION/EXCLUSION CRITERIA

DDM Inclusion and Exclusion Criteria					
Inclusion Criteria	Exclusion Criteria				
-Age 50 years or older -English speaking -Admitted to the intensive care unit (medical or surgical) -Expected mechanical ventilator support for ≥48 hours -Consentable through a legally authorized representative -Have access to a telephone	-History of dementing illnesses and other neurodegenerative diseases such as Alzheimer's disease or vascular dementia -Psychiatric illness which is not well controlled -Alcohol withdrawal symptoms/concern for withdrawal -Suspected or confirmed drug intoxication/overdose -Traumatic brain injury, ischemic or hemorrhagic cerebrovascular accident, or undergoing neurosurgery -Uncorrected hearing or vision impairment including legal blindness -Incarcerated at the time of study enrollment -Enrolled in another clinical trial which does not permit co-enrollment				
	-Any medical condition precluding safe use of headphones such as: skin breakdown, burns, facial or skull fractures				

5. ENROLLMENT and RANDOMIZATION

Clinical Settings and Study Population: Patients will be recruited from two Indianapolis Hospital systems: Eskenazi Health and Indiana University Health. Patients will also be recruited from Mayo Clinic Rochester.

Recruitment Targets: Final study sample will comprise 160 mechanically ventilated older adults ≥50 years of age.

Screening and Enrollment: Research staff will review the electronic medical records of ICU patients daily for eligibility. Eligible patients' clinical teams will be approached if necessary to confirm eligibility. Eligible individuals (those who meet inclusion criteria and do not meet any exclusion criteria) will be screened up to twice per day for delirium until approached for the study using the CAM-ICU-7. Once eligibility is confirmed, the research team will approach patients or their legally authorized representatives for consent depending on patients' clinical status. Patients consented through their legally authorized representative will be reconsented once clinically able.

Randomization: Using a computer-generated list of random numbers created by study statistician, participants will be randomized by permuted block with varying block sizes. Randomization will occur after consent in a 1:1 manner and will be stratified based on hospital location.

6. STUDY PROCEDURES

Interventions: For up to seven days, enrolled subjects will either receive 1) one-hour music listening sessions twice daily through noise-cancelling headphones, or 2) one-hour sessions consisting of a silence track twice daily through noise-cancelling headphones.

a. Music Intervention: Twice daily one-hour intervention will be delivered based on our extensive playlist created by our board-certified music therapist consultant and used in our previous studies. The playlist contains relaxing slow tempo instrumental music (60-80 beats/minute). Featured instruments in the playlist include piano, harp, reed, guitar and Native American flute. The mix features classical music and relaxing melodies and does not contain lyrics or spoken words. In addition to the twice daily music intervention sessions, patients will be encouraged to self-initiate listening to slow-tempo music from the study playlist whenever desired as a means to engage in quiet time or listening enjoyment. Our iPad® app will efficiently log all of the 'as desired' music listening sessions by automatically capturing frequency, length, and music selections for both the twice daily music intervention sessions as well as the self-directed listening sessions. Variability in self-directed music listening duration and frequency will be used as a covariate in subsequent analyses.

b. Attention Control: A silence only track will be added to the study iPads® and will be activated in the form of an app similar to the music listening tracking app. Patients randomized to this arm will receive a noise cancellation headphone-applied condition identical to the music intervention experimental treatment; twice daily one hour-sessions. Likewise, patients will have the opportunity to use the silence app with headphones whenever desired. As with the music intervention, the app will track each session's length, frequency, and self-directed headphone application with the silence track.

[figure not shown]
Delivery of the Intervention: The research manager will ensure good operating status of the iPad[®] music app, headphones and connectivity to the tracking portal prior to the initiation of the intervention. Both the experimental and the attention control conditions will be delivered through identical iPads[®] with our music tracking app and noise cancellation headphones to ensure blinding of group assignment when study staff perform assessments. All patients will receive two one-hour sessions daily between the hours of 0900 to 1200, and from 1300 to 2000. Nurses will receive training to minimize distractions at that time, such as turning off televisions and avoiding non-essential patient care. Patients will receive standard ICU care per local practices including the ABCDEF bundle, 21,22 which is part of routine care at participating ICUs. Patients will continue to receive clinical care for delirium based on their primary clinical team's discretion.

Blood Sample Collection

We will collect blood samples prior to first intervention session (up to 10ml in tubes containing anticoagulant), at day 3, and at the end of the intervention period (up to 10 ml in tubes containing anticoagulant). The samples will be transported to the CTSI lab, and will be prepared and stored using deidentified labels. Samples will be stored for future biomarker analysis which includes measurement of pro-inflammatory and anti-inflammatory cytokines, reactive oxygen species and DNA damage, proteomics, epigenetics, and protein-gene associations.

Blinding: Apart from the patient and research staff member assigning the music intervention, all study personnel and clinical staff interacting with the patient will remain blinded to each patient's intervention assignment throughout enrollment, follow-up and data analysis.

Study Flow: Eligible patients or their legally authorized representatives will be approached immediately after fulfilling the inclusion criteria. The intervention will start immediately post-enrollment depending on the time of enrollment. If enrolled prior to 1100, subjects will receive both one-hour music sessions on day of enrollment, if enrolled after 1200; they will receive a single one-hour music session on day of enrollment. If enrollment occurs after 2000, sessions will be started the following day. Study staff will assess for delirium, pain, and anxiety for the whole duration of ICU stay or until day 28 if the patient remains in the ICU. Cognition, depression and anxiety measures will be collected at three months post-hospital discharge in both intervention and control groups. See Figure 3 for study flow and outcomes assessment.

Outcomes Assessments: Trained and blinded research assistants will complete in-hospital and post- hospital outcomes assessments consisting of measures of delirium, cognition, pain, depression and anxiety. Data will be

collected using Research Electronic Data Capture (REDCap). We will employ multiple techniques to ensure concealment of outcomes assessment. 73,74 Our research assistants are trained not to inquire about study assignments. The research randomization staff member will deliver the intervention and the research assistants will not be aware of the intervention assignments. Subjects and their family members will be instructed not to discuss their intervention with the research assistants. All research staff undergoes a comprehensive training program with respect to outcomes assessments that has been employed in our prior trials. We will train the research staff on conducting sedation, delirium, delirium severity, pain, anxiety, depression and cognition assessments utilizing the same teaching methods. The PIs and Co-I will oversee the relevant training. [name] and [name] will do the didactics and bedside teachings and certifications of all the research staff for sedation, delirium, pain, anxiety, and depression assessments. [name] will train and certify the research staff on cognition assessments.

Outcomes Measures: In-Hospital Outcomes:

- **Delirium/Coma Free Days:** Delirium/coma free days will be the primary outcome for the trial. Delirium/coma free days are the number of days after randomization patients are alive free of delirium and not in coma during the seven-day study intervention phase. This outcome describes the duration of normal cognitive status where the patient is not comatose and does not have delirium and has been utilized in high impact studies. 14-17 We will utilize the Confusion Assessment Method for the ICU (CAM-ICU)75 and the Richmond Agitation Sedation Scale (RASS)⁷⁶ for assessment of delirium and coma respectively. RASS score ranges from -5 to +4 with a score of -4 or -5 (lack of response to verbal or physical stimuli) characterized as comatose and ineligible for CAM-ICU assessments. RASS scores of -3 and -2 depict moderate and light sedation, -1 drowsiness, 0 alert and calm, and +1 to +4 various degrees of agitation. Patients with a RASS score of -3 to +4 will be considered eligible for CAM-ICU assessments. The CAM-ICU score will be determined by examining the patient for (a) acute or fluctuating changes in mental status, (b) inattention, (c) altered level of consciousness and (d) disorganized thinking. Patients will be considered delirious if they display (a), (b), plus (c) and/or (d). Trained research assistants will be performing CAM-ICU twice daily after the assigned intervention. Sedation status through RASS will be collected before and after the intervention delivery. After the 7-day study intervention phase, study staff will continue to assess RASS and CAM-ICU twice daily throughout the subject's hospital stay (up till day 28).
- **2. Delirium Severity**: Delirium severity will be assessed twice daily by trained research assistants using the CAM-ICU-7 developed by [name]. CAM-ICU-7 is a seven-point scale (0-7), derived from the RASS and the CAM-ICU. The CAM-ICU-7 score ranges from 0-7; categorized as 0-2: no delirium, 3-5: mild to moderate delirium, and 6-7: severe delirium. Trained research assistants will be performing CAM-ICU-7 twice daily after the assigned intervention. After the 7-day study intervention phase, study staff will continue to assess CAM-ICU-7 twice daily throughout the subject's hospital stay (up till day 28).
- **3. Pain:** Pain will be assessed by trained research assistants utilizing the Critical Care Pain Observation Tool (CPOT), a valid and reliable instrument in critically ill patients with and without delirium, ^{78,79} recommended by the SCCM 2018 PADIS guidelines. ²¹ CPOT uses observable physiological and behavioral indicators of pain to determine whether pain is present and can be used in nonverbal patients. It contains 4 sections, each with different behavioral categories, including facial expressions, body movements, muscle tension, and either compliance with ventilator (intubated patients) or vocalization (non-intubated patients). The score ranges from 0-2 for each section with a total score range of 0-8 with higher scores indicating more pain. Trained research assistants will be performing CPOT four times daily before and after intervention delivery. We will continue to assess CPOT twice daily after the 7-day study intervention phase throughout the ICU stay.
- **4. Anxiety:** Anxiety intensity defined as a heightened state of apprehension, agitation, and arousal, ⁸⁰ will be measured four times daily before and after assigned intervention using a 100-mm Visual Analog Scale-Anxiety (VAS-A), which measures changing anxiety and is amenable to intervention. ^{81,82} The VAS-A will be presented to all patients vertically, like a thermometer, and will be anchored on the ends by 0 = not anxious at all and 100 = most anxious ever. The VAS-A is scored using a ruler from the 0 anchor to the mark placed by the patient, which yields the current level of anxiety from 0 to 100. The same ruler will be used to score all VAS-As for consistency. [name] has used the VAS-A extensively in prior research studies, including a vertical orientation of the instrument that is sensitive and easier for critically ill patients to see, resulting in very little missing data on this important variable. ^{31,81-83} We will continue to assess VAS-A twice daily after the 7-day study intervention phase throughout the ICU stay.

Post-Hospital Discharge Outcomes:

1. Cognition: Cognition will be measured by 4 objective tests of memory, attention, information processing speed, and executive cognitive function (Auditory Verbal Learning Test [AVLT], Digit Span, and Symbol Digit Modalities Test [SDMT], and Controlled Oral Word Association test [COWA]) using a telephone-based administration format, the Indiana University Telephone-Based Assessment of Neuropsychological Status (IU-TBANS) at 3-months post hospital discharge. Previous research has demonstrated that these tests can be delivered reliably and precisely by telephone. ⁸⁴ The AVLT is a 5-trial 15-item word list learning task that provides two scores: sum recall of the five learning trials and delayed recall. Digit Span measures working memory and the ability to repeat short random number sequences forward and backward. We will use the oral version of the SDMT. Participants will be mailed the SDMT response sheet prior to the assessment and told to keep the envelope sealed and at hand for the day of the assessment. At the day of the assessment, the participant will be

instructed to open the envelope and the SDMT practice items will be completed. Total score is the number of correct numbers-symbol pairings called out in 90 seconds. The COWA is a measure of verbal fluency and executive cognitive function in which words are generated orally that begins with specified letters of the alphabet. Scores derived from these tests can be analyzed separately and also combined to form a single cognitive composite score. We will provide participants with pre-assessment instructions to structure the assessment to minimize distraction and interruption and maximize reliability and precision.

2. Depression and Anxiety: We will use the Patient Health Questionnaire—9 (PHQ-9)^{85,86} and Generalized Anxiety Disorder Scale (GAD-7)^{87,88} to determine the impact of the music intervention on ICU survivors' mood and anxiety. The PHQ-9 is a nine-item depression scale with a total score from 0 to 27 and the GAD-7 is a seven-item anxiety scale with a total score from 0 to 21. Both of these scales are derived from the Patient Health Questionnaire, have good internal consistency, test-retest

Demographics (Age, race, gender, education, insurance)	Method of Collection	Enrollment	ICU Phase			
(Age, race, gender, education,	EMR	Enrollment			Hospital Discharge	Post-Hospital Discharge Phase
(Age, race, gender, education,	EMR		Intervention Phase	Post-intervention Phase		3 months
		Х				
Clinical data (lab values)	EMR	X	Daily			
Comorbidities (Charlson) ^a	EMR	X				
Baseline cognitive function (IQCODE) ^b	Caregiver interview	x				
History of depression, anxiety	EMR	X				
Diagnoses	EMR	X			X	
Severity of Illness ^c (APACHE II, SOFA)	EMR	X (APACHE)	Daily (SOFA)			
Functional Status ^d (ADL, IADL)	EMR	X				
Medications ^c (sedatives, analgesics, anxiolytics, antipsychotics)	EMR, patient, caregiver	X	Daily	Daily	X	X
Duration of Mechanical Ventilation, Length of ICU and Hospital Stay	EMR				х	
Mortality	EMR				X	X
Discharge Disposition	EMR				X	
ABCDEF bundle adherence	EMR, Nursing reports	х	Daily	Daily		
Intervention characteristics	iPad App and Web Portal	X	х			
Physiologic Parameters (respiratory rate, heart rate, blood pressure)	EMR	х	4XDaily	Daily		
Delirium, Pain, Anxiety ^f (RASS, CAM-ICU, CAM-ICU- 7, CPOT, VAS-A)	Direct Assessment		2XDaily (CAM-ICU, CAM-ICU-7) 4XDaily (RASS, CPOT, VAS-A)	2XDaily		
Cognition (IUTBANS) ^g	Direct Assessment					X
Mood symptoms ^h (GAD-7, PHQ-9) Healthcare Utilization	Direct Assessment					X

^aChronic comorbidities measured through Charlson Comorbidity Index⁸⁹, ^bIQCODE: Informant Questionnaire on Cognitive Decline in Elderly⁹⁰, ^cSeverity of Illness measured through APACHE II⁹¹ and SOFA⁹², ^cFunctional Status measured through Katz and Lawton Scales^{33,94}, ^cAnlgesic and sedative exposure is defined as aggregate measure of pain and sedation intensity and the drug frequency in a 24 hour period. We will aggregate dose frequency and dosing intensity by each enrollment day. A dose frequency analysis will be used⁹⁵⁻⁹⁷, ^cBASS; Richmond-Agitation Sealation Scale⁷⁶, CAM-ICU: Confusion Assessment Method in the ICU⁹⁷, CPOT: Critical Care Pain Observation Tool⁷⁸, VAS-4: Visual Analog Scale-Anxiety^{31,8} IUTBANS: Indiana University Telephone-Based Assessment of Neuropsychological Status⁸⁴; ^bPHQ-9: Patient Health Questionnaire⁸⁵, GAD-7, Generalized Anxiety Disorder Scale⁸⁷; ^c Captured through Indiana Network for Patient Care (INPC)

reliability as well as construct, criterion, procedural and factorial validity for the diagnosis of major depression and general anxiety disorder.⁸⁵⁻⁸⁸ Research staff will collect PHQ-9 and GAD-7 over the phone at 3 months post-hospital discharge.

Other Data Measures: The table above shows other data measures including physiologic parameters of respiratory rate, heart rate, blood pressure (collected four times daily before and after assigned intervention during the 7-day intervention phase; daily afterwards during ICU stay) and timeline of data collection. We will also collect the post-extubation ICU Recall Prior to/around Discharge. The Intensive Care Experience (ICE) questionnaire will be administered to all subjects and contains 25 total questions in four main categories: awareness of surroundings, frightening experiences, recall of experiences, and satisfaction with care.

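### As-desired headphone use is encouraged in the music arm but only made available in the control arm, so prompting, and possibly headphone time, may differ along with the music

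*Combined protocol and SAP*

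**What the plan says.** Section 3 (Study Design) sets the question as music against a silence-track attention control. Section 6 (Study Procedures) then describes two layers of headphone use.

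- **Scheduled use** is the same in both arms. Under Delivery of the Intervention: "All patients will receive two one-hour sessions daily between the hours of 0900 to 1200, and from 1300 to 2000". The control is described as a "noise cancellation headphone-applied condition identical to the music intervention experimental treatment; twice daily one hour-sessions".
- **As-desired use** is described arm by arm. For music, in addition to the scheduled sessions, "patients will be encouraged to self-initiate listening to slow-tempo music from the study playlist whenever desired"; the reasons given are quiet time and enjoyment. For control: "Likewise, patients will have the opportunity to use the silence app with headphones whenever desired".

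Use is logged in both arms. The app captures scheduled and self-directed music sessions, and for control "the app will track each session's length, frequency, and self-directed headphone application with the silence track". The music paragraph adds that variation in self-directed music listening will serve as a covariate in later analyses. No counterpart is described for control headphone time. The primary ANCOVA (Statistical Considerations, Primary Specific Aim) names group and unbalanced baseline demographics, and neither form of self-directed use.

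**The concern.** An attention control is there to equalise everything but the active ingredient: contact with staff, the device, and time set aside for rest. Encouraging a patient is something a person does; offering an opportunity is only access. As worded, the first is written for one arm and the second for the other. No common script, number of prompts or staff role is given.

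If this is carried out as written, two things besides music could separate the arms. One is the prompting itself. The other is any additional time under noise-cancelling headphones that the prompting produces. Quiet time, one of the two reasons given for encouraging music patients, is also available from a silence track under the same headphones, so that reason does not explain prompting one arm only.

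What is at stake is interpretation. The primary aim concerns the efficacy of music, and a positive result would leave open how much of the effect came from prompting or extra quiet. That extra noise-cancelled time affects delirium is plausible, but the documents do not show it. The imbalance in prompting does not depend on it.

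**Working it through.** The plan gives no amount, target or cap for as-desired use, so there is no figure of its own to reproduce. The sample size (128 complete, 160 enrolled) is not in question and does not change.

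**Step 1: scheduled exposure.** The inputs are two one-hour sessions a day, for at most seven days (Section 6).

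Scheduled hours = 2 × 1 × 7 = 14 in each arm, a difference of 0. This is a maximum, since late enrollment on day one, death, discharge or transfer out of the ICU reduces it.

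Any imbalance in headphone time must therefore come from as-desired use.

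**Step 2: as-desired exposure, by assumption.** Let m and c be self-directed hours a day in the music and control arms, over a full seven days.

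Total for music = 14 + 7m; total for control = 14 + 7c; ratio = (14 + 7m) / (14 + 7c).

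| m (h/day) | c (h/day) | Music total (h) | Control total (h) | Difference (h) | Ratio |
|---|---|---|---|---|---|
| 0 | 0 | 14 | 14 | 0 | 1.00 |
| 0.25 | 0 | 15.75 | 14 | 1.75 | 1.125 |
| 0.5 | 0 | 17.5 | 14 | 3.5 | 1.25 |
| 1 | 0 | 21 | 14 | 7 | 1.50 |
| 1 | 0.5 | 21 | 17.5 | 3.5 | 1.20 |
| 1 | 1 | 21 | 21 | 0 | 1.00 |
| 2 | 0 | 28 | 14 | 14 | 2.00 |
| 2 | 1 | 28 | 21 | 7 | 1.33 |

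Every m and c here is an assumption. Equal use at any level gives no difference. Control use shrinks the ratio: half an hour more a day in music gives 1.25 if controls take none, and 1.20 if they take half an hour. The table covers only music use at or above control use; the documents do not rule out the reverse.

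**Step 3: can the analysis repair it?** Self-directed use is recorded after randomization. It may depend on the arm, through prompting and through liking for the content. It also depends on the patient's state, because a comatose or delirious patient cannot readily start a session, and days free of coma and delirium are the primary outcome. Conditioning on such a variable would not isolate a music effect. The planned covariate is also described for music listening only. Neither route removes a difference in prompting, so the remedy has to lie in delivery.

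**The case against.** The strongest reply is that this is loose wording rather than a planned difference. The control sentence opens with a word that signals parity, scheduled time is equal, and optional use is open to and logged in both arms. Self-initiated listening is also a described part of the intervention, so intention to treat compares the packages as designed. Ventilated patients may in any case start few extra sessions. Much of this stands, and it limits the point to attribution. It does not remove it: if parity is intended, the operative verbs do not deliver it, and sites could follow them literally.

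A reader might infer four stronger things that the documents do not support.

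- *That headphone time does differ.* No usage figure is given or forecast. A difference is a possible consequence only.
- *That the plan contradicts its own claim of an identical control.* That word describes the headphone condition and is followed directly by the twice-daily sessions. It is not applied to as-desired prompting.
- *That staff are instructed to prompt repeatedly.* The sentence is passive and names no role or frequency. A single remark at set-up would fit it.
- *That nurses or assessors would be unblinded.* Section 6 has the randomization staff member deliver the intervention, exempts the person assigning it from blinding, uses identical equipment, and tells patients and families not to discuss it with assessors. Encouragement by that unblinded person fits the text. Disclosure would arise only if someone meant to be blinded gave an arm-specific prompt, which the plan does not say.

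**Conclusion.** The point holds in a limited form. As written, encouragement for extra sessions is specified for music and not for control, so prompting would differ by arm if the text is followed literally, and self-directed headphone time may differ too. The size is unknown. Under the assumed range it runs from no difference to 14 extra hours over seven days (28 against 14), and the upper end requires two hours a day of extra music with no extra control use.

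The randomized comparison of the two packages stays valid. It would go too far to say that a positive result could tell us nothing about music; the narrower conclusion is that the effect could not be attributed fully to music. The correction should be made because it is cheap and sharpens the trial's stated question, not because the design fails without it.

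**What to change.** In Section 6, describe as-desired use in the same terms for both arms: one content-neutral wording that refers to the headphone session without naming what is played, the same prompt frequency, and the same staff role. State who gives the prompt, so that it sits clearly within the blinding arrangements.

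Report self-directed and total headphone minutes by arm from the app log, descriptively, to show whether the control was matched in practice. Do not rely on adjusting the primary comparison for these minutes.

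The cost is a sentence in each arm's description, a short bedside script and one descriptive table. The app already records use in both arms, and sample size, visits and the primary model are unchanged. The small downside is that as-desired music use may fall slightly if the common prompt is milder than the present encouragement.
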